1 PROTOCOL SUMMARY

1.1 Synopsis

Title:	Analysis of the immune response to COVID-19 vaccination and outcomes in individuals with and without immune deficiencies and dysregulations
Study Description:	
This prospective cohort study will assess the pre- and post-vaccination immune responses in individuals with select immunodeficiencies and immune dysregulations compared to healthy volunteers who receive a coronavirus disease 2019 (COVID-19) vaccine, as well as any adverse events (AEs) experienced after vaccination. All required study visits for this protocol may be conducted remotely; in-person visits at the NIH are optional. Subjects who have not yet been vaccinated will undergo baseline blood sampling using finger stick microsamplers and/or venous blood draw within 7 days prior to receiving the vaccine. Additional samples will be requested from participants approximately 14-21 days after dose 1 and 21-28 days after dose 2 (if applicable). Optional samples may be collected at 6, 12, and 24 months post-vaccination. If subsequent booster doses are received while a participant is still on study, blood samples will again be requested approximately 28 days after each booster dose, through the 5th Covid-19 vaccine dose received, and then participants may proceed with the optional 6-, 12-, and 24-month follow-up sample collection. Participants who are able to attend in-person visits at NIH will have optional on-site blood draws 1 and 3 days after doses 1 and 2 (as applicable). Research evaluations will include baseline severe acute respiratory syndrome-coronavirus-2 (SARS-CoV-2) antibody titers to the spike (S), nucleocapsid (N), and receptor binding domain (RBD) proteins, to assess pre-vaccination SARS-CoV-2 exposure and evaluate responses to vaccination. Additional immune markers of interest may include presence of autoantibodies, transcriptomic profiling, T-cell receptor (TCR) repertoire, among others. Participants who only submit finger stick home microsamplers at the timepoints listed above will be evaluated for SARS-CoV-2 antibody titers and autoantibodies only. All subjects will be asked at baseline about prior COVID-19 diagnosis, symptoms, and severity, and will be asked additional questions at follow-up timepoints (including after additional booster doses) about vaccine AEs using standardized questionnaires.

Primary Objective:	To characterize the immune response to COVID-19 vaccination among immunodeficient and immune dysregulated individuals compared to healthy volunteers.
Secondary Objectives:	
• To characterize the COVID-19 vaccine-associated AEs among immunodeficient and immune dysregulated individuals compared to healthy volunteers.
Exploratory Objectives:	
• Assess the relationship between prior SARS-CoV-2 infection and vaccine-induced immune response.• To characterize pre-vaccine COVID-19 disease prevalence and severity among immunodeficient and immune dysregulated individuals.• To assess induction, strength, and durability of T- and B-cell-specific immune responses to SARS-CoV-2 (as measured by frequency and diversity of SARS-CoV-2 specific T and B cell clonotypes and titers of specific antibody responses), and their correlation to the underlying immune deficiency/dysregulation.• To characterize autoantibodies present in immunodeficient and immune dysregulated individuals before and after COVID-19 vaccination.• To assess the incidence of post-vaccination breakthrough SARS-CoV-2 infection and to determine the SARS-CoV-2 virus genomic sequence in such cases.
Primary Endpoint:	Change in S and RBD immunoglobulin G (IgG) antibody titer from baseline to 14-21 days or 21-28 days (depending on vaccine manufacturer and platform) after vaccine dose 1, and 21-28 days after dose 2 and any subsequent doses (depending on vaccine manufacturer and platform).
Secondary Endpoints:	
• Incidence of vaccine-associated AEs experienced by immunodeficient individuals compared to healthy volunteers.
Exploratory Endpoints:	
• Characterization of post-vaccine immune response and AEs in patients with antibody evidence of prior SARS-CoV-2 infection• Pre- and post-vaccination incidence of COVID-19-associated symptoms experienced in individuals with immune deficiency/dysregulation who are positive for SARS-CoV-2 by serology or diagnostic polymerase chain reaction (PCR).• Characterize how various forms of immune deficiency or dysregulation impact generation, strength, and durability of T- and B-cell responses.

- Incidence of autoantibodies pre- and post-COVID-19 vaccination comparing individuals with immune deficiency/dysregulation to healthy volunteers.
- Incidence and genetic sequence of post-vaccination SARS-CoV-2 infection as reported by patient and confirmed by PCR and sequencing.

Sample Size: N=500 (n=400 with immune deficiency/dysregulation, n=100 healthy volunteers)

Accrual Ceiling: N=600

Study Population: We will enroll individuals 3 years of age and older who are receiving COVID-19 vaccination outside of this study. Affected study participants must have evidence of a primary or secondary immune deficiency or dysregulation as documented on another NIAID protocol or by an outside physician. Control participants will be healthy volunteers, and may include unaffected relatives of immunodeficient/dysregulated participants.

Description of Sites/Facilities Enrolling Participants: This is a single-site study being conducted at the NIH Clinical Center (CC) via in-person and remote visits. Subjects may be recruited from existing NIH protocols. They may also be referred from community practitioners who see this population. Healthy volunteers may also be recruited through the NIH Clinical Research Volunteer Program, the Office of Patient Recruitment, MMG Patient Recruitment, ResearchMatch, or BuildClinical. Individuals may be enrolled in person or remotely.

Study Duration: 4 years

Participant Duration: Up to 24 months from participant's last vaccine dose. This may be extended for participants who receive additional booster doses and agree to additional extension visits, up to 2 years after the booster vaccination, through the 5th dose only.

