^^Due to the ongoing pandemic, venous blood draws may be conducted at the NIH or at off-site facilities (e.g., subjects' private physicians, Quest laboratories). Subjects will be provided microsampler kits for at-home fingerstick sample collection. Venous blood draw will be waived for participants who are unable to obtain one at any given timepoint. Microsamples will not be collected at on-site visits, as the small volume needed can be taken from another tube.

††May not be drawn at every visit, per PI discretion based on the participant's underlying immunodeficiency and study timepoint.

†If the subject opts in for the optional follow-up, then the final study visit will be the last visit that the participant chooses to have.

‡‡Participants will be sent optional saliva collection kits to return to the NIH bi-weekly for PCR and genetic sequencing of the virus. Participants whose samples are PCR positive will be asked to submit an additional COVID-19 symptom questionnaire and will be referred for care as needed. Each time a participant receives an additional booster dose while they are still on study, they may participate in optional bi-weekly saliva collections for an additional 6-month period.

§Optional additional visits for participants having specimens drawn at NIH only.

¶Only 1 sample type is required for off-site visits (either Mitra microsampler or plasma isolation). Plasma isolation is the preferred sample type.

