The aims of this study are to characterize the immune response to COVID-19 vaccination, the number and type of vaccine-associated AEs, and pre- and post-vaccine COVID-19 disease prevalence and severity in individuals with different types of immune defects. Potential diseases of interest that are followed at NIAID include those with neutrophil dysfunction such as chronic granulomatous disease and leukocyte adhesion deficiency; combined immune deficiencies such as DOCK8 (dedicator of cytokinesis 8) deficiency, leaky severe combined immunodeficiencies (SCIDs; e.g. RAG (recombination-activating gene) deficiency), X-linked immunodeficiency with magnesium defect, Epstein-Barr virus infection, and neoplasia (XMEN) disease (T-cell deficiency), STAT3 (signal transducer and activator of transcription 3) deficiency (Hyper IgE syndrome), defects of the PI3K (phosphoinositide 3-kinase) pathway; predominantly B lymphocyte defects such as X-linked agammaglobulinemia and common variable immune deficiency (CVID); defects of the Interleukin 12 (IL-12)/Interferon gamma (IFNg)/STAT1 pathway; *GATA2* deficiency; and those with immune activation such as neonatal-onset multisystem inflammatory disease (increased inflammasome activity) and autoimmune polyendocrinopathy-candidiasis-ectodermal dystrophy (APECED).

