3 OBJECTIVES AND ENDPOINTS

Objectives	Endpoints	Justification for endpoints
Primary		
To characterize the immune response to COVID-19 vaccination among immunodeficient and immune dysregulated individuals compared to healthy volunteers.	Change in S and RBD IgG antibody titer from baseline to 14-21 days or 21-28 days (depending on vaccine manufacturer and platform) after dose 1, and 21-28 days after dose 2 and any subsequent doses (depending on vaccine manufacturer and platform).	It is of interest to understand the changes in anti-SARS-CoV-2 antibody levels induced by vaccination in individuals with immune deficiency/dysregulation.
Secondary		
To characterize the COVID-19 vaccine-associated AEs among immunodeficient and immune dysregulated individuals compared to healthy volunteers.	Incidence of vaccine-associated AEs experienced by immunodeficient and immune dysregulated individuals compared to healthy volunteers.	It is of interest to understand the safety (by knowing the incidence of AEs) of COVID-19 vaccines in individuals with immune deficiency/dysregulation.
Exploratory		
Assess the relationship between prior SARS-CoV-2 infection and vaccine-induced immune response.	Characterization of post-vaccine immune response and AEs in patients with antibody evidence of prior SARS-CoV-2 infection compared to those without evidence of prior infection.	Because so many people have had SARS-CoV-2 infections prior to vaccination, it is of interest to understand whether this affects the immune response to vaccination.

To characterize pre-vaccine COVID-19 disease prevalence and severity among immunodeficient and immune dysregulated individuals.	Incidence of COVID-19-and associated symptoms experienced in individuals with immune deficiency/dysregulation who are positive for SARS-CoV-2 by serology or diagnostic PCR.	It is of interest to understand the incidence and clinical presentation of COVID-19 in individuals with immune deficiency/dysregulation, especially as COVID-19 is an inflammatory-mediated disease.

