Additional research evaluations include analysis of the nature, diversity, and frequency of SARS-CoV-2 specific T- and B-cell receptor clonotypes. These evaluations will be used to assess pre-vaccination SARS-CoV-2 exposure and expected response to vaccination. Additional research evaluations may include virus neutralization assays to assess antibody functional response, flow cytometry, and transcriptome and genetic analyses. Comparisons of the immune response will be made among immunodeficiency/dysregulation subtypes and against healthy controls. This will allow characterization of the differences in post-vaccination immune responses and AE presentation.

Subjects will be asked at baseline about prior COVID-19 diagnosis, symptoms, and severity using standardized questionnaires. This will allow us to characterize the different manifestations of COVID-19, potentially including a lack of hyper-inflammatory symptoms associated with severe disease due to dysregulation of the immune response that will be present in many of the study participants. To conduct active screening for post-vaccination COVID-19 infections, participants will be sent optional saliva collection kits to return to the NIH bi-weekly for 6 months, for PCR and genetic sequencing of the virus. Participants whose samples are PCR positive will be asked to submit an additional COVID-19 symptom questionnaire and will be referred for care as needed. Each time a participant receives an additional booster dose while they are still on study (through the 5th COVID-19 vaccine a person receives), they may participate in optional bi-weekly saliva collections for an additional 6-month period. Since this is optional, saliva samples received outside of the requested windows are acceptable and will be analyzed at the discretion of the PI. At follow-up timepoints, participants will be asked about all possible vaccine-related AEs, which will be particularly important given recent information about possible vaccine-induced anaphylaxis.

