8.4 Statistical Analysis

Multiple sets of analyses will be done to characterize the immune response in each of the groups of participants with immune deficiency/dysregulation:

1. Within-group: Estimate the vaccine response at each timepoint relative to baseline within an immune deficiency/dysregulation group.
2. Longitudinal between-groups: Compare the vaccine response profiles of different groups at sampling times.
3. Adjusted analyses controlling for SARS-CoV-2 infection.

For symptoms: focus will be on estimation of the proportion of symptoms that are present or absent in these individuals. Variables will be presented by frequency distribution (e.g. frequency counts, percentages, and 95% confidence intervals). In addition, this study will be used as the basis for hypothesis generation to explore disease manifestations in individuals with different types of immune deficiency/dysregulation if the number of enrolled individuals allow.

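### COVID-19 cases are found differently before and after vaccination, so the two symptom proportions are not comparable, and the bias can run either way

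*Combined protocol and SAP*

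**What the plan says.** The exploratory endpoint in Section 1.1 covers "Pre- and post-vaccination incidence of COVID-19-associated symptoms experienced in individuals with immune deficiency/dysregulation who are positive for SARS-CoV-2", where positivity may be serological or by diagnostic PCR. The aims at the end of Section 2.2 likewise include "pre- and post-vaccine COVID-19 disease prevalence and severity in individuals with different types of immune defects".

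Section 3 is narrower. Its objective is "To characterize pre-vaccine COVID-19 disease prevalence and severity among immunodeficient and immune dysregulated individuals", and its endpoint is "Incidence of COVID-19-and associated symptoms experienced in individuals with immune deficiency/dysregulation who are positive for SARS-CoV-2 by serology or diagnostic PCR", with no mention of a post-vaccination period. The synopsis lists the same pre-vaccine objective beside its two-period endpoint.

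Case-finding before vaccination:
- Recall: "Subjects will be asked at baseline about prior COVID-19 diagnosis, symptoms, and severity using standardized questionnaires" (Section 4.1).
- Earlier tests and symptoms taken from records or by history (Section 7.2).
- Baseline S, N and RBD serology, which the synopsis says serves to assess earlier exposure.

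Case-finding after vaccination:
- Optional saliva kits returned bi-weekly for 6 months, renewable after a booster (Sections 1.2 and 4.1). On a positive result, "Participants whose samples are PCR positive will be asked to submit an additional COVID-19 symptom questionnaire".
- Infections reported by the participant, which count towards the separate breakthrough endpoint. Section 7.2 lists the symptom form as due after infection but sets no interval.

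For the analysis, Section 8.4 states that "focus will be on estimation of the proportion of symptoms that are present or absent in these individuals", with counts, percentages and 95% confidence intervals. It does not split cases by route of detection. Hypothesis 5 in Section 8.1 concerns symptom prevalence and severity across immune subgroups and healthy volunteers.

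**The concern.** A symptomatic share is a proportion of detected infections, so it depends on which infections are detected. An outside test is often sought because of symptoms and tends to miss silent infection. Serology and saliva screening can both find silent infection, but serology is the added route before vaccination and saliva screening the added route after it. The mix of cases can therefore change between periods even if the illness does not.

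Serology also does not work equally in all subgroups. Section 2.2 says that people with common variable immunodeficiency do not make antibody, and Section 8.3 expects poor antibody responses in two groups. Participants who enrol after vaccination may have no pre-vaccine sample at all (Section 4.1), which for this purpose is the same as serology that detects nothing.

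Two readings are at stake. Pre- and post-vaccination figures shown together invite a conclusion about vaccination and symptoms. Under hypothesis 5, subgroups may appear to differ in symptoms when they differ only in whether serology can reveal their silent infections.

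**Working it through.** The plan gives no expected proportion, case count or precision for this endpoint, so there is no figure to reproduce. The check asks what the planned proportions would show if vaccination had no effect on symptoms.

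**Inputs, all assumed because the documents give none**
- Silent share of infections: a = 0.35 in both periods (varied below).
- Outside testing or self-report finds 60% of symptomatic and 10% of silent infections, in both periods.
- Baseline serology finds a fraction q of past infections, symptomatic or silent: q = 0 or 0.8.
- Saliva PCR finds 80% of infections in those who take part. With uptake u, it finds v = 0.8u overall.
- No case enters by serology after vaccination. S and RBD antibody are then the vaccine-response measures, and the plan does not say whether N antibody alone defines a post-vaccination case.

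**Formula.** Let x be the detection probability of the added route (q before, v after), acting independently of outside testing.
- Symptomatic infections detected: S = 1 − 0.4(1 − x).
- Silent infections detected: A = 1 − 0.9(1 − x).
- Apparent symptomatic share = (1 − a)S / [(1 − a)S + aA].

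**Before vaccination**
- q = 0: S = 0.60, A = 0.10; 0.390 / (0.390 + 0.035) = 91.8%.
- q = 0.8: S = 0.92, A = 0.82; 0.598 / (0.598 + 0.287) = 67.6%.

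**After vaccination**
- u = 30%, v = 0.24: S = 0.696, A = 0.316; 0.4524 / (0.4524 + 0.1106) = 80.4%.
- u = 50%, v = 0.40: S = 0.76, A = 0.46; 0.494 / (0.494 + 0.161) = 75.4%.
- u = 100%, v = 0.80: S = 0.92, A = 0.82; 67.6%.

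**Apparent change, after minus before, with no vaccine effect**

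| Saliva uptake | Serology detects 0% | Serology detects 80% |
|---|---|---|
| 30% | −11.4 points | +12.8 points |
| 50% | −16.3 points | +7.8 points |
| 100% | −24.2 points | 0 points |

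The same function applies in both periods, so in this model the sign depends only on whether q is below or above v. There is a false fall if q < 0.8u, a false rise if q > 0.8u, and no change if they are equal. With no saliva uptake there is no fall at any q.

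**Sensitivity to the silent share** (uptake 30% to 100%)
- a = 0.20: −6.2 to −14.2 points at q = 0; +8.0 to 0 at q = 0.8.
- a = 0.50: −16.9 to −32.8 points at q = 0; +15.9 to 0 at q = 0.8.

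**Between subgroups, before vaccination only.** 91.8% − 67.6% = 24.2 points between a subgroup in which serology detects nothing and one in which it detects 80%, although the true share is 65% in both.

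**The case against.** The strongest reply is that the plan makes no pre/post comparison. The stated objective is pre-vaccine, Section 3's endpoint does not mention a post-vaccination period, hypothesis 5 compares subgroups rather than periods, and Section 8.4 is descriptive and meant for hypothesis generation. This largely stands: no test or vaccine-effect claim is planned, which limits the priority. It does not remove the point, because the synopsis endpoint and the Section 2.2 aims still put both periods together. The subgroup problem also needs no pre/post contrast.

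A reader might infer that symptoms will appear to fall after vaccination. The documents do not support a fixed direction. Serology belongs to the case definition and can find silent infections before vaccination. Saliva collection is optional, and self-reported infections continue to enter afterwards. The false fall needs weak serology combined with real saliva uptake.

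A reader might also add a further fall because some people complete the form before symptoms begin. The form is requested only after the sample has been returned and tested, and nothing in the documents says what fraction would still be pre-symptomatic. The missing interval is a gap, but its effect cannot be sized.

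Finally, the no-serology case is an extreme. Section 8.2 plans 40 participants with predominantly antibody deficiencies, and only those infected enter the endpoint. That limits the reach of the largest figures, though late enrolees without a stored sample are in the same position.

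**Conclusion.** The concern holds as a lack of comparability, not as a predicted fall. Case-finding differs between periods, serology is likely to differ in sensitivity between subgroups, and Section 8.4 does not separate cases by route. With 35% of infections silent and the detection rates assumed above, the false change at 30% to 100% saliva uptake is about −11 to −24 points where serology finds nothing and about +13 to 0 points where it finds 80%. The false pre-vaccine difference between two such subgroups is about 24 points (92% against 68%). These sizes are illustrations. The documents give none of the inputs, and the sign turns on serology sensitivity and saliva uptake. A false fall is most plausible in antibody-deficient participants. The synopsis and Section 3 also disagree on whether the endpoint covers the post-vaccination period. Low priority, since the endpoint is exploratory and descriptive.

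**What to change.** - In Section 8.4, report symptom proportions by route of detection (outside test or self-report; study saliva screening; serology only) within each period and immune subgroup. Add a source-of-detection field to support this, and say whether N antibody alone defines a post-vaccination case.
- State that no vaccine effect on symptoms will be inferred from the pre- and post-vaccination figures.
- Send or repeat the post-vaccination symptom form at one fixed interval after any positive test, including infections diagnosed outside the saliva programme. Section 7.2 already allows a form after infection.
- Reconcile the synopsis endpoint and the Section 2.2 aims with the pre-vaccine objective and the endpoint in Section 3.

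Do not rest a pre/post statement on cases found by symptom-prompted testing. Nearly all of them are symptomatic by construction in both periods, so the proportion could not show a difference.

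The cost is some analysis wording, one data field and one timed REDCap form. Strata will be smaller and their confidence intervals wider.

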1.2 Schedule of Activities

Evaluation	Study Day (window)							
	Screening and Baseline*	Vaccine dose 1 Follow-up			Vaccine dose 2 Follow-up [‡]			Optional Follow-up [†]
	-7 to 0	1 day after vaccination [§]	3 days after vaccination [§]	14-21 OR 21-28 days after vaccination ^{**}	1 day after vaccination [§]	3 days after vaccination [§]	21-28 days after vaccination ^{**}	6, 12, and 24 months (±2 weeks) after last vaccination
Informed consent	X							
Clinical Procedures and Evaluations								
COVID-19 history and symptom questionnaire	X							
Baseline medical history and screening questionnaire	X							
Changes in medical history questionnaire				X			X	X
Electronic AE questionnaire [^]				X			X	
Behavioral questionnaire							X	
Clinical Laboratory Evaluations ^{^^}								
Blood Volume (mL)								
CBC with differential	3 mL	4 mL	4 mL	3 mL	4 mL	4 mL	3 mL	
TBNK lymphocyte phenotyping/flow/cytok		[X]	[X]		[X]	[X]		

Research Laboratory Evaluations ^{^^}	Blood Volume (mL)							
	0.8 mL	0.8 mL	0.8 mL	0.8 mL	0.8 mL	0.8 mL	0.8 mL	0.8 mL
Mitra microsampler [¶] 
 SARS-CoV-2 antibody (S, RBD, N – IgG, IgM, IgA) Autoantibodies 	0.8 mL			0.8 mL			0.8 mL	0.8 mL
Serum (red cap) ^{††} 
 Neutralizing SARS-CoV-2 antibodies 	5 mL	5 mL	5 mL	5 mL	5 mL	5 mL	5 mL	5 mL
Plasma isolation (EDTA purple cap) [¶] 
 DNA isolation (for high throughput sequencing of TCR/BCR repertoire and for genetic studies) 	10 mL	10 mL	10 mL	10 mL	10 mL	10 mL	10 mL	10 mL
PAXgene tube ^{††} 
 Whole blood RNA 	2.5 mL	2.5 mL	2.5 mL	2.5 mL	2.5 mL	2.5 mL	2.5 mL	2.5 mL
PBMC isolation (sodium heparin green top OR EDTA purple cap) ^{††} 
 Lymphocyte/plasmablast Functional T cells 	10 mL	10 mL	10 mL	10 mL	10 mL	10 mL	10 mL	10 mL
Saliva ^{‡‡} 
 SARS-CoV-2 PCR and sequencing 	Bi-weekly through 6 months							
Daily Blood Volume	31.3 mL	31.5 mL	31.5 mL	31.3 mL	31.5 mL	31.5 mL	31.3 mL	31.3 mL
Cumulative Blood Volume	31.3 mL	62.8 mL	94.3 mL	125.6 mL	157.1 mL	188.6 mL	219.9 mL	251.2 mL (6 mos.) 282.5 mL (12 mos.) 313.8 mL (24 mos.)

[X] = will be performed with portion of sample collected for CBC with differential and does not require additional volume.

Abbreviations: AE, adverse event; BCR, B cell receptor; CBC, complete blood count; COVID-19, coronavirus disease 2019; DNA, deoxyribonucleic acid; EDTA, ethylenediaminetetraacetic acid; Ig, immunoglobulin; PBMC, peripheral blood mononuclear cell; N, nucleocapsid; RBD, receptor binding domain; RNA, ribonucleic acid; S, spike; SARS-CoV-2, severe acute respiratory syndrome coronavirus 2; TBNK, T, B, and natural killer (cells); TCR, T cell receptor; NP, nasopharyngeal; OP, oropharyngeal; PCR, polymerase chain reaction.

*Baseline sampling and questionnaire can happen on the day of vaccination as long as it is prior to receiving the dose. Participants may enroll after vaccination was already performed. If these individuals do not have current plans for an additional booster dose, previous timepoint samples will not be obtained and they will proceed with the next relevant sampling timepoint. In this situation, if stored blood samples from studies in which subjects are concurrently enrolled are available, they will be used. If stored samples are not available, these samples will be considered waived. If these individuals plan to receive an additional booster vaccination(s), they will be enrolled prior to the booster dose and follow the normal schedule, including a baseline draw prior to the booster.

**The exact timing of these visits will depend upon vaccine manufacturer and platform (as detailed in the Manual of Procedures) but will fall within the ranges indicated. For subjects who decline participation in the optional long-term follow-up visits, study completion will end after the dose 1 or 2 follow-up visit(s), depending on whether the subject received a 1-dose or 2-dose vaccine. Each time a participant receives an additional booster dose while they are still on study, a 21-28-day visit will be performed, and optional long-term follow-up visits will be offered. Samples will be requested from participants as scheduled after each vaccination and booster (+/- 7 days) however samples received outside of the requested windows are acceptable and will be analyzed at the discretion of the PI.

‡ Not all vaccines require a second dose and therefore these follow-up timepoints will be not applicable for participants receiving those vaccines.

^AE questionnaire will be administered after any additional booster dose.

^^Due to the ongoing pandemic, venous blood draws may be conducted at the NIH or at off-site facilities (e.g., subjects' private physicians, Quest laboratories). Subjects will be provided microsampler kits for at-home fingerstick sample collection. Venous blood draw will be waived for participants who are unable to obtain one at any given timepoint. Microsamples will not be collected at on-site visits, as the small volume needed can be taken from another tube.

††May not be drawn at every visit, per PI discretion based on the participant's underlying immunodeficiency and study timepoint.

†If the subject opts in for the optional follow-up, then the final study visit will be the last visit that the participant chooses to have.

‡‡Participants will be sent optional saliva collection kits to return to the NIH bi-weekly for PCR and genetic sequencing of the virus. Participants whose samples are PCR positive will be asked to submit an additional COVID-19 symptom questionnaire and will be referred for care as needed. Each time a participant receives an additional booster dose while they are still on study, they may participate in optional bi-weekly saliva collections for an additional 6-month period.

§Optional additional visits for participants having specimens drawn at NIH only.

¶Only 1 sample type is required for off-site visits (either Mitra microsampler or plasma isolation). Plasma isolation is the preferred sample type.

